12.3. UNSCHEDULED EVENTS

12.3.1. Withdrawal

Clinicians involved in the trial should not withdraw participants from the trial unless it is harmful (ethically, physically or mentally) for the participant to continue or they pose a risk to staff.

In the event that a participant withdraws their participation in the trial prior to randomisation, no further data is required to be submitted.

In the event that a participant withdraws after randomisation they will be requested to attend follow-up visits and provide follow-up data including participant questionnaires, if they consent to do so.

If a participant explicitly states they do not wish to attend follow-up visits and / or contribute further data to the trial or to complete any further participant questionnaires this should be treated as a withdrawal from the trial.

The PI or delegate must make every effort to ensure that the specific wishes of any participant who wishes to withdraw consent for intervention or further involvement in the trial are documented using the Withdrawal Request CRF in order that the correct processes are followed by the CTRU and research site following the withdrawal of consent.

12.3.2. Pregnancy

Any suspected or confirmed pregnancies from the date of randomisation until the end of the follow up at month 24 must be recorded on the Notification of Pregnancy CRF and reported to the CTRU by fax or secure file transfer within **7 calendar days** of the research site becoming aware.

If the suspected or confirmed pregnancy occurs before the date of surgery the operation will not go ahead. It is the responsibility of the treating surgeon to decide what course of action should be taken in relation to ensuring the participant's ongoing treatment outside of the trial protocol.

All other trial procedures can be maintained with the participant's consent. All known pregnancies should be followed up until final outcome.

12.3.3. Death

All deaths occurring between a participant's randomisation day and the last day of follow up (i.e. 24 months post-surgery) must be recorded on the Notification of Death CRF and sent to the CTRU within **7 calendar days** of the site research team becoming aware of the death. Data collected will include but not be limited to:

- Date of death
- Cause of death

12.4. PARTICIPANT COMPLETED QUESTIONNAIRES

Participants will complete a number of health-related quality of life questionnaires (see Section 11). Where questionnaires are completed in clinic, an authorised member of the trial team will check that the forms have been completed fully and will be able to provide clarification only if requested by the participant. Staff will be trained to avoid directing patients in their responses. All questionnaires will be completed during clinic visits except at month 6, when the CTRU will send questionnaires to participants either by post or online according to participant consent and preference. Participants will provide details for the method of contact they consent to and express a preference for contact method on the contact details CRF.

Where a participant has expressed a preference to receive their questionnaires by post only: a second set of questionnaires will be posted to participants if the first set of questionnaires are not returned within 2 weeks.

Where the participant has expressed a preference to receive their questionnaires online: participants will receive an email containing an online link to complete their questionnaires, after which a further email reminder containing an online link will be sent one week after the first email if they have not completed the questionnaires. Where a participant has also given permission to receive postal questionnaires and does not respond to the first two emails, then they will be posted the questionnaires at 2 weeks.

Where the participant has consented to a text reminder: participants will be sent a text reminder confirming that the questionnaires have been posted/ online link sent to them and a further text reminder one week after the first text if the questionnaires have not been returned by post or completed online.

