12.1. SUBMISSION OF TRIAL DATA

Participating research sites will be expected to submit original paper CRFs to the CTRU at the University of Leeds and retain copies of all completed CRFs for the trial in the Investigator Site File. Following receipt, the CTRU will contact trial sites to resolve any missing or discrepant data. Any outstanding CRFs will be requested by the CTRU until received or until the data is confirmed as unavailable. All trial x-rays will be transferred to the CTRU using the secure file transfer service. For full details of the imaging requirements and process please refer to the radiography manual.

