Adjusted estimates of the treatment effect will be estimated from multivariable regression modelling of the KOOS pain score at 12 months. Statistical significance of non-inferiority of KJD relative to KR will be based on a 2-sided likelihood-based test with a type 1 error of 2.5% in both tails, assuming KOOS pain scores (or transformed scores if appropriate) are normally distributed and adjusted by baseline score at the time of randomisation and stratification factors (delivery unit and OA severity). If the 95% confidence interval for the absolute difference in means between KJD and KR lies entirely below or includes the non-inferiority boundary (see Section 14.2) then there would be insufficient evidence to reject the null hypothesis that KJD is inferior to KR. Conversely, if the 95% confidence interval lies entirely above the non-inferiority boundary then there would be evidence to reject the null hypothesis and conclude KJD is non-inferior to KR. Further modelling will include confounders of age and BMI, observing and addressing non-linearity through use of fractional polynomial transformation. Secondary analyses of the primary outcome measure will be considered. If non-inferiority is demonstrated and KJD appears superior to the KR, based on estimated effect and CI, statistical significance for superiority will be calculated based on an ITT analysis with similar modelling strategy. A secondary analysis of the primary outcome measure will be based on random effects multilevel modelling to account for the nested and longitudinal structure of the data over the full 24 months follow-up.

ANALYSES OF SECONDARY OUTCOME MEASURES

Analysis of PROMs (KOOS components, OKS, Pain VAS and EQ5D-3L) will focus on reporting the pre-specified dimensions of the individual questionnaires. Questionnaire responses will be combined and transformed into dimension scores, according to scoring manuals where these exist, presented graphically and longitudinally. Standardised area under the curve statistics will be compared across treatment groups as an analysis conditional on patient survival.

Range of motion and timed up and go functional assessments will be reported descriptively.

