14.2. SAMPLE SIZE

Sample size and power calculations are based on a non-inferiority hypothesis for the primary outcome measure. Secondary outcome measures are not powered. The statistical design is based on a distribution-based method informed by data from the previous trial (16), clinical co-applicant experience and consensus, reported recommendations of minimally important differences in knee disease and feedback from the PPI focus group. A median 12-point credible minimal difference (range 4 to 20) for patient reported KOOS pain has been recommended (19) and 13-points for patients with knee OA (42). This is supported by patients who report they would accept a 10-15% (translated to 10-15 points) increase in pain to retain their knee. Based on this consensus for a minimally important difference, the non-inferiority threshold is defined to be at least 33% less at a threshold of 8. Previous observational studies of KOOS pain have reported variability (SD) from 15 to 21 (3,43–45).

A one-sided significance of 2.5% is used which allows two-sided 95% confidence intervals to be presented. The target recruitment is based on demonstrating non-inferiority within a limit of 8 points. Ignoring drop-out within 12-months, 146 patients recruited to each group would have 90% power to demonstrate non-inferiority within a threshold of 8 points and variability assumed SD=21. Allowing for 15% dropout, the target is inflated to 172 patients in each group resulting in an overall recruitment target of 344 patients. The underlying assumptions of the statistical design will be monitored by the DMEC.

No sample size adjustment has been made to accommodate surgeon learning curve since external fixation is a common procedure which orthopaedic surgeons are frequently required to do for trauma.

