17. DATA MONITORING

Data will be monitored for quality and completeness by the CTRU. Missing data will be requested until it is received, confirmed as not available or the trial is at the analysis stage. Missing data items will not be requested from participants over and above the principles laid out in Section 12.4. The CTRU and Sponsor reserve the right to intermittently conduct source data verification exercises on a sample of participants, which will be carried out by staff from the CTRU or Sponsor. Source data verification will involve direct access to patient notes at the participating hospital sites and the ongoing central collection of copies of consent forms and other relevant investigation reports.

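### The protocol states no remote route for the month-12 KOOS, the primary outcome, when a participant misses the clinic visit and cannot be rebooked within the window

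*Protocol*

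**What the plan says.** On where questionnaires are completed, protocol Section 12.4 states: "All questionnaires will be completed during clinic visits except at month 6, when the CTRU will send questionnaires to participants". The schedule in Section 12.2 agrees. Month 6 is the only follow-up by post or online. Months 3, 12 and 24 are clinic visits, with windows of +/- 4, 6 and 8 weeks.

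The reminder steps in Section 12.4 concern forms that are sent out. For postal participants, "a second set of questionnaires will be posted to participants if the first set of questionnaires are not returned within 2 weeks". Online participants get an email link, a reminder after one week and, if they have agreed to post, a paper set at two weeks. Text reminders are also provided for. As written, these steps serve month 6.

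On missing data, Section 17 makes two statements. The first is general: "Missing data will be requested until it is received, confirmed as not available or the trial is at the analysis stage". The second limits it: "Missing data items will not be requested from participants over and above the principles laid out in Section 12.4". Section 12.1, which is addressed to sites, adds: "Any outstanding CRFs will be requested by the CTRU until received or until the data is confirmed as unavailable".

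The primary analysis in Section 14.1 depends on the month-12 form: "Adjusted estimates of the treatment effect will be estimated from multivariable regression modelling of the KOOS pain score at 12 months". Section 14.2 allows for loss as follows: "Allowing for 15% dropout, the target is inflated to 172 patients in each group".

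**The concern.** The recovery effort is placed at the wrong time point. Month 6 is not the primary time point, yet it has a full chase by post, email and text. Month 12 carries the primary outcome and has only the clinic visit. KOOS is self-administered and, by the protocol's account in Section 11.1, typically takes 10 minutes, so nothing about the instrument requires attendance. The contact details CRF already records each participant's consented and preferred contact method.

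Section 12.3.1 treats an explicit wish not to attend follow-up visits and/or not to give further data as withdrawal from the trial. A participant who would fill in a form at home but does not want to return to clinic has no written option.

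Two things are at stake. One is precision: the sample size has little slack beyond its 15% allowance. The other is bias: the trial is open-label, and attendance at month 12 could plausibly relate to pain or to treatment arm, although the protocol has no data on either.

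**Working it through.** **1. What the sections provide together.** Section 12.4 fixes clinic completion at months 3, 12 and 24. Its chasing steps apply to forms sent out, which means month 6. Section 17 ties requests to participants to 12.4, and 12.4 contains no chasing step for a clinic form. Section 12.1 has the CTRU pursue sites. The one remaining route to a missed month-12 KOOS is to rebook the visit inside the window, and nothing forbids that. If rebooking fails, no route is stated.

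**2. The plan's own sample size.** Inputs from Section 14.2: margin 8, SD 21, one-sided 2.5%, power 90%, dropout 15%. A true difference of 0 is assumed.

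- Normal approximation: n = 2 × [21 × (1.960 + 1.282) / 8]² = 144.8, so 145 per arm.
- Noncentral t: power is 89.8% at 145 and 90.0% at 146, so 146 per arm.
- Inflation: 146 / 0.85 = 171.8, so 172 per arm and 344 in total.

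The plan's figures reproduce.

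**3. Power if more month-12 scores are missing.** The number analysed per arm is 172 × (1 − missing fraction). Power is from the noncentral t, with noncentrality 8 / (21 × √(2/n)). Rates above 15% are assumptions.

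| Missing at month 12 | Analysed per arm | Power |
|---|---|---|
| 15% (planned) | 146.2 | 90.1% |
| 20% (assumed) | 137.6 | 88.3% |
| 25% (assumed) | 129.0 | 86.2% |

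The normal approximation gives about 0.2 points more (90.3%, 88.5% and 86.4%). SD 21 is the top of the range of 15 to 21 in Section 14.2. With SD 18, 129 per arm still gives about 94%. The calculation ignores any gain from baseline adjustment.

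**4. Bias from informative loss.** Let f be the fraction missing in an arm and g the amount by which attenders' mean score exceeds that of non-attenders. The arm's full mean is (1 − f) × A + f × (A − g), where A is the attenders' mean. Using attenders alone therefore overstates the arm by f × g. The bias in KJD minus KR is f(KJD) × g(KJD) − f(KR) × g(KR). With an assumed g of 10 points in both arms:

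| Loss in the two arms | Bias (points) | Share of the 8-point margin |
|---|---|---|
| 15% and 15% | 0.15 × 10 − 0.15 × 10 = 0 | 0% |
| 20% and 10% | 0.20 × 10 − 0.10 × 10 = 1.0 | 12.5% |
| 15% and 0% | 0.15 × 10 − 0 = 1.5 | 19% |

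If g ranges from 5 to 15, the last row runs from 0.75 to 2.25 points. KOOS is scored with 100 as no symptoms. If non-attenders have more pain, heavier loss in the KJD arm flatters KJD and moves the estimate towards non-inferiority. Heavier loss in the KR arm does the reverse.

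**The case against.** A reader might infer that Section 17 forbids asking participants again, so that anyone who misses month 12 is lost to the primary analysis. The text does not support this. The limiting sentence follows directly on one saying that missing data will be pursued. It speaks of missing data items, does not clearly cover a whole missed visit, and does not stop a site rebooking within a 12-week span. Loss of primary data is a risk, not something the protocol states.

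Clinic collection is also a reasoned choice. Range of movement and the timed up and go test take place at the same visit, and staff check forms for completeness. Exclusion criterion 12 screens out people unable to attend follow-up or complete questionnaires. Those who withdraw after randomisation are still approached, subject to their consent: "In the event that a participant withdraws after randomisation they will be requested to attend follow-up visits and provide follow-up data including participant questionnaires". The 15% allowance exists to absorb loss, and part of that loss, such as deaths and full withdrawals, could not be recovered by a posted form. Section 14.1 foresees possible imputation, sensitivity analyses under different missing-data assumptions, and a longitudinal model over 24 months.

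All of this stands and limits the size of the problem. It does not supply the missing route. Imputation and modelling are weaker than an obtained score when missingness depends on pain itself, and rebooking does not help a participant who will not or cannot come back.

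**Conclusion.** The gap is real and modest. The protocol collects the primary outcome in clinic only, reserves its remote procedure for month 6, and adds no remote route in Section 17. The sample size is correct and is not in question.

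The power cost is about 2 points at 20% missing and about 4 points at 25%. Both rates are assumed, and the figures use the conservative SD of 21. The bias figures rest on an assumed 10-point gap and vanish when loss and its relation to pain are the same in both arms. A 1.5-point shift needs all the informative loss to fall in one arm, which the documents give no reason to expect. No estimate can be made of how many scores a remote form would recover. The point is therefore a cheap improvement to data collection, not an error that must be corrected before the trial can be relied on.

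**What to change.** In Section 12.4, keep clinic completion as the default at months 3, 12 and 24. Add that if a participant's month-12 questionnaires have not been received by a set day inside the window, the CTRU sends them, KOOS first, by the existing month-6 post, online and text procedure. Apply the same rule at months 3 and 24.

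Choose the day so that the procedure can finish. The second posting comes at 2 weeks. If 2 further weeks are allowed for return (an illustrative figure), the first set must go out at least 4 weeks before the window closes. At month 12 that is no later than 2 weeks after the due date. The other windows differ in length and need their own day.

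Align the limiting sentence in Section 17 so that it plainly permits these requests, and record the mode of completion on each form.

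The cost is a short amendment and more use of a system the CTRU already runs. The downside is mixed-mode completion for a minority of month-12 scores, which a sensitivity analysis by mode can check.

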12.5. DEFINITION OF END OF TRIAL

The end of the trial is defined as the date of the last participant's last data item corresponding to the 24 month follow-up time point.

13. SAFETY REPORTING

For the purpose of this surgical trial the safety reporting terms adverse events and serious adverse events have been translated into complications and serious complications.

13.1. GENERAL DEFINITIONS

A **complication** is defined as an untoward medical event in a participant which has a causal relationship with the trial. This includes the trial intervention (KR or KJD surgery) and any subsequent treatment relating to the trial intervention (such as treatment of complications caused by the trial intervention and any trial-specific interventions e.g. the consent process and completion of questionnaires).

An untoward medical event can include:

- any unintentional unfavourable clinical sign or symptom;
- any new illness or disease of the deterioration of an existing condition;
- any clinically relevant deterioration in any clinical tests.

A **serious complication** (SC) is defined as a complication which meets at least one of the following criteria:

- results in death;
- is life-threatening¹;
- requires hospitalisation or prolongation of existing hospitalisation;
- results in persistent or significant disability;
- consists of a congenital anomaly or birth defect;
- is otherwise considered medically significant by the Investigator.

¹ Life-threatening refers to an event in which the participant was at risk of death at the time of the event, NOT an event which hypothetically may have caused death had it been more severe.

An **Unexpected Serious Complication** (USC) is a serious complication that is **related** and **unexpected** and will require expedited reporting to enable reporting to the main Research Ethics Committee (REC) and Sponsor. KARDS protocol $v1.0_{-}190927$

The Health Research Authority (HRA) defines the terms '**related'** and '**unexpected'** as:

- '**Related':** that is, it resulted from the administration of any of the research procedures. All complications are by definition related to the trial procedures (untoward medical events which are unrelated to the trial procedures are not being collected in this trial).
- 'Unexpected': that is, the type of event that in the opinion of the investigator is not considered expected. Examples of expected complications are provided in Section 13.2.2; note this is not an exhaustive list.

Medical and scientific judgement must be exercised in deciding whether an event is serious (see protocol Section 13.3 for Responsibilities). These characteristics / consequences must be considered at the time of the event and do not refer to an event which hypothetically may have caused one of the above.

13.2. RECORDING AND REPORTING COMPLICATIONS

Information on all complications will be collected for this trial whether volunteered by the participant, discovered by investigator questioning or detected through physical examination or other investigation.

13.2.1. Classification of complications

All post-surgery complications should be graded using the Clavien-Dindo classification scale (37) where appropriate (see Appendix 2).

13.2.2. Expected complications – standard reporting

The following is a list of expected complications related to the administration of any research procedure including pre and post-operative complications associated with either surgical procedure or the use of general anesthetic and any further interventions on the affected knee (but are not limited to):

- Complex regional pain syndrome in the affected leg
- Anaesthesia reactions
- Stiffness in the affected leg needing manipulation under anaesthesia
- Pain in the affected leg
- Neuro-vascular injury in the affected leg

KARDS protocol v1.0_190927
- Compartment syndrome in the affected leg
- Infection needing topical, oral or systemic antibiotics
- Infection needing surgical intervention (details of surgical intervention to be provided on a separate form including the organism identified, treatment given, duration of symptoms and current status)
- Revision surgery in the affected leg
- Failure of external fixator frame or pins (breakage / cut out / loosening) (KJD arm only)
- Myocardial infarction
- Angina
- Pneumonia
- Pulmonary embolism
- Any other cardio-pulmonary event needing further treatment
- Cerebro-vascular accident (stroke)
- Fracture in non-affected limb

All expected complications will be reported from randomisation to end of follow-up on standard CRFs.

As the above complications, including those which fulfil the criteria of seriousness, are expected within the trial population they will not be subject to expedited reporting to the main REC. They will however, be included in the annual safety report provided to the main REC.

13.2.3. All other complications – standard reporting

Information about the incidence and severity of all other complications (this includes all non-serious expected and non-serious unexpected complications) which occur from the date of randomisation to end of follow-up will be recorded on standard CRFs. These events will **not** be subject to expedited reporting requirements.

13.2.4.Serious Complications and Unexpected SeriousComplications – expedited reporting

The following (SCs) and USCs occurring within 24 months of surgery are subject to expedited reporting and must therefore be notified to CTRU **within 24 hours** of the clinical research staff becoming aware of the event:

- Symptomatic venous thrombo-embolism
- Osteomyelitis
- Fracture in affected limb
- Death within 6 weeks of surgery

Notifications must be sent to CTRU by fax or secure file transfer using the SC / USC CRF. Once all resulting queries have been resolved the CTRU will request the original form is posted to CTRU and a copy retained at site.

24 hr fax for reporting SC & USCs: [name] or

[contact]

For each SC and USC the following data will be collected:

- Start and end dates (if resolved)
- Full details of complication in medical terms with a diagnosis (if possible)
- Action / intervention
- Outcome
- An identifiable and authorised reporting source (i.e. the signature of the investigator or other medic authorised by the investigator at the reporting research site).

Any follow-up information on SCs and USCs must be faxed or sent by secure file transfer to the CTRU as soon as it is available. Events will be followed up until resolution or a final outcome has been reached. All USCs will be reviewed by the Chief Investigator (CI) and will be subject to expedited reporting to the Sponsor and the REC

by the CTRU on behalf of the CI in accordance with current HRA guidance, CTRU Standard Operating Procedures (SOPs) and Sponsor requirements.

